The primary aim of the analysis is to estimate the true rate of favorable outcome at one year after their first transplant in all eligible subjects for whom induction for an islet transplant is begun. The observed favorable outcome rate and a one-sided 95% exact binomial confidence interval will be used to estimate the true favorable outcome rate. The primary analysis will compute a one-sided exact binomial test of the null hypothesis that the true rate is less than or equal to 27% versus the alternative that the true rate exceeds 27% (see sample size justification). The analysis will be considered to support efficacy if the null hypothesis is rejected at the 5% level of significance. The lower bound for the confidence interval p_L will be determined as the value that satisfies the following equation:

$$0.05 = \sum_{x \geq r} \binom{24}{x} p_L^x (1 - p_L)^{24-x}$$

The rates of favorable outcome and exact one-sided 95% confidence intervals will be computed for each contributing center.

Statistical Analysis Plan

This analysis will be conducted for the ITT population. The primary endpoint should be available for all treated subjects. An exception will be if a death occurs, if the subject withdraws consent to be followed, or if immunosuppression is begun but the subject never receives a transplant. In these cases the endpoint will be classified as failure to achieve a favorable outcome. Should the endpoint not be evaluated for a particular individual for other reasons, a failure will be imputed unless an evaluation is done at a time longer than one year after transplant, in which case, that later value will be imputed. All imputations will be reported with the primary analysis. The rates and the exact one-sided 95% confidence intervals for complete data and imputed data will be compared to ascertain the sensitivity of the imputation.

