10.2.1 Analysis of Key Secondary Endpoints

Because this is a single intervention study, the tests will be one sided tests for whether the true rates are greater than the endpoint's' predetermined "minimum rate for efficacy". These minimum rates were determined by the investigators to be large enough to have credibility for the islet transplant community. The minimum rate for efficacy is provided in Table 10.1 for each of the key secondary outcomes.

Statistical Analysis Plan

Table 10.1: Key Secondary Outcomes and Minimum Rates for Efficacy

	Key Secondary Outcome	Minimum Rate for Efficacy
1	At 365 ± 14 days after the last islet transplant (the primary at 365 days after the last transplant): The proportion of subjects with both an HbA1c ≤ 6.5% and an absence of severe hypoglycemic events from Day 28 to Day 365, or a reduction in HbA1c of 1 point and an absence of severe hypoglycemia from Day 28 to Day 365.	50%
2	At 365 ± 14 days after the first islet transplant: The proportion of subjects with HbA1c < 7.0% and free of severe hypoglycemic events from Day 28 to Day 365.	50%
3	At 365 ± 14 days after the first islet transplant: The proportion of subjects free of severe hypoglycemic events from Day 28 to Day 365.	50%
4	At 365 ± 14 days after the first islet transplant: The proportion of subjects with HbA1c < 7.0%.	50%
5	At 365 ± 14 days after the first islet transplant: The proportion of subjects with HbA1c ≤ 6.5%.	50%
6	The proportion of subjects with a reduction in HbA1c of at least 1 point	50%
7	At 365 ± 14 days after the first islet transplant: The proportion of insulin-independent subjects.	20%
8	At 365 ± 14 days after the first and last islet transplant: The change from baseline in the Clarke score.	Favorable increase of 1 point

As with the primary endpoint, the key secondary endpoints should be available for all transplanted subjects and the analysis will be conducted for the ITT population. If an endpoint is

Statistical Analysis Plan

not available for a transplanted subject then it will be imputed using the same rules that were used for the primary endpoint. That is the measure will be imputed as a failure unless later data would make the outcome a success.

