10.2.2 Additional Efficacy Endpoints

Excluding the first key secondary endpoint, the additional efficacy endpoints are just the key secondary endpoints measured at one year, two years, and three years after the first and after the last islet transplant. They will be analyzed in exactly the same way as the key secondary endpoints but no adjustment will be made for multiple comparisons. The secondary endpoints that are not directly related to the primary and key secondary efficacy endpoints are discussed in detail in the following sections.

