12.5 Sensitivity Analysis

Measurements of secondary endpoints may be missing at any time point. In our analysis report for the secondary endpoints, we will not impute missing values in the analysis but will report results for the observed data only. With close monitoring and data validation, the chance of having missing values will be minimized except that some serious adverse events (SAEs) may force subjects to withdraw from the study treatment or withdraw consent without a particular reason during the study. The interpretation of our analysis is strictly applied to the efficacy measurable population. However, a sensitivity analysis will be performed to determine the potential effect that missing values have on the analyses of the secondary endpoints.

Missing values due to SAE will be excluded from this analysis. The analysis on these subjects will be provided in SAP section 14.

We will conduct a sensitivity analysis assuming a missing at random mechanism: *i.e.*, we assume that a subject will withdraw consent at random with probability r . This probability will be estimated at each time point.

We will use the method of multiple imputation (Schafer, 1999) to develop estimates and standard errors that account for the missing data. We will compare the magnitude of the differences between multiple imputation estimates and observed data estimates to assess the potential affect

Statistical Analysis Plan

of the missing data. The assumption of missing at random cannot be verified and these results must be viewed with caution.

13. Other Exploratory Analyses

13.1 *Change from baseline*

For each secondary outcome and time point where it is appropriate, we will explore the change from baseline over time. The endpoints and time points are as follows:

- insulin requirements (measured quarterly years 1 and 2 post-first and post-last transplant then every 6 months until year 3 post-last transplant)
- HbA1c (measured at day 28 and then quarterly years 1, 2, and 3 post-first and post-last transplant)
- Clarke Score (measured at 6 months and year 1 post-first and post-last transplant then every 6 months until year 3 post-last transplant)
- β score (measured quarterly year 1 post-first transplant, quarterly years 1 and 2 post-last transplant then every 6 months until year 3 post-last transplant)
- Basal glucose (measured quarterly year 1 post-first transplant, quarterly years 1, 2, and 3 post-last transplant)

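### The key and additional binary secondary endpoints carry two incompatible missing-data rules, and the sensitivity analysis leaves out values missing because of SAEs

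*SAP*

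**What the plan says.** Section 10.2.1 analyses the key secondary endpoints in the ITT population. When one is unavailable it applies the primary endpoint's rules, summarised as: "the measure will be imputed as a failure unless later data would make the outcome a success". Section 10.2.2 extends this to the additional efficacy endpoints at one, two and three years: "They will be analyzed in exactly the same way as the key secondary endpoints", apart from the multiplicity adjustment.

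Section 12.5 speaks of secondary endpoints without excepting the key or additional ones: "we will not impute missing values in the analysis but will report results for the observed data only". It limits interpretation to subjects whose efficacy can be measured, a population that section 5.2 does not define.

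On sensitivity, 12.5 says: "We will conduct a sensitivity analysis assuming a missing at random mechanism", using multiple imputation. It then sets one group aside: "Missing values due to SAE will be excluded from this analysis". For those subjects it gives a pointer: "The analysis on these subjects will be provided in SAP section 14".

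**The concern.** For a key or additional binary endpoint, one rule keeps a subject without data in the denominator as a failure and the other removes that subject. The estimated rate, its confidence limit and its p-value all depend on which section the analyst follows. In an open-label, single-arm trial of 24 subjects, that choice could be made, and defended, after the data are known.

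The planned sensitivity analysis would not expose the effect. Section 12.5 itself names SAEs as a reason why subjects may withdraw, yet it removes values missing for that reason. Section 14, to which it refers those subjects, contains safety summaries (AE incidence, severity, attribution, resolution, immune sensitization) and no efficacy analysis.

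**Working it through.** **Calibration on the plan's own figure.** Section 4 gives 24 subjects, a one-sided 5% exact binomial test and a null rate of 27%, with about 90% power at 57% and 80% at 52%. The smallest r with P(X ≥ r | 24, 0.27) ≤ 0.05 is r = 11, with exact size 0.0369. Power is P(X ≥ 11 | 24, 0.57) = 0.9045 and P(X ≥ 11 | 24, 0.52) = 0.7907. Both reproduce the stated values, so the same exact test is used below.

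**Inputs.** N = 24 (section 4). Minimum rates are 50% for key endpoints 1 to 6 and 20% for insulin independence (Table 10.1). The test is exact, one-sided binomial, with Benjamini-Hochberg over 8 hypotheses at q* = 0.1 (section 10.2.1). The thresholds i/8 × 0.1 are 0.0125, 0.025, 0.0375, 0.05, 0.0625, 0.075, 0.0875 and 0.1. The number missing, m, is an assumption (0 to 4), and none of the missing subjects is taken to have a later success.

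**Formula.** With x successes, p = P(X ≥ x | n, p0). Under 10.2.1, n = 24. Under 12.5, n = 24 − m.

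Minimum rate 50%:

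| Successes | Failure imputed (n = 24) | Observed, m = 1 | m = 2 | m = 3 | m = 4 |
|---|---|---|---|---|---|
| 15 | 0.1537 | 0.1050 | 0.0669 | 0.0392 | 0.0207 |
| 16 | 0.0758 | 0.0466 | 0.0262 | 0.0133 | 0.0059 |
| 17 | 0.0320 | 0.0173 | 0.0085 | 0.0036 | 0.0013 |

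Two entries written out:
- 15 of 20: (15504 + 4845 + 1140 + 190 + 20 + 1)/2^20 = 21700/1048576 = 0.0207.
- 16 of 20: 6196/1048576 = 0.0059.

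Minimum rate 20%, 8 successes: 0.0892 with failure imputed, against 0.0431 (m = 3) and 0.0321 (m = 4) on observed data.

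**Effect on the Benjamini-Hochberg decision.**
- 15/24 (p = 0.1537) exceeds the largest threshold, 0.10, and can never be rejected. 15/20 (p = 0.0207) fails the first threshold but is rejected once at least two of the eight hypotheses are.
- 16/24 (p = 0.0758) is rejected only if at least seven of the eight are (0.075 < 0.0758 ≤ 0.0875). 16/20 (p = 0.0059) passes even the strictest threshold.
- The procedure is step-up, so one changed p-value can also alter the decision on other endpoints.

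**Coverage of the sensitivity checks.** Section 10.1 promises that rates and intervals "for complete data and imputed data will be compared to ascertain the sensitivity of the imputation", but states this for the primary endpoint. Section 13.1 uses multiple imputation for exploratory change-from-baseline models. That leaves 12.5 as the only stated sensitivity analysis for the secondary binary endpoints, and it excludes the SAE-related missing values.

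**The case against.** The strongest reply is that the sections can be reconciled. Section 2.3.2 separates key from other secondary endpoints, 10.2.1 gives a specific rule for the key ones, and 10.2.2 extends it and leaves the unrelated endpoints to the sections that follow, where 12.5 sits. The ITT statement in section 5.2 and the denominator of 24 in section 8.2 also fit failure imputation. This is the better reading, but the SAP does not state it, and 12.5 is worded to cover all secondary endpoints.

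Several stronger inferences should be resisted:
- A reader might infer that every secondary proportion is affected. The cut-offs for MAGE, LI, HYPO and Clarke score of 4 or more have only the observed-data rule, so no conflict arises there.
- A reader might infer that graft failures drop out of the denominator. Graft failure alone does not make HbA1c or hypoglycemia data missing, and section 5.1.1 treats such subjects as failures.
- A reader might equate multiple imputation under missing at random with the observed-data analysis. It can draw on other observed data, so the two need not agree, and 12.5 itself cautions that the assumption cannot be verified. The defect is the SAE exclusion and the lack of any not-at-random check.

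Section 10.2 also calls the secondary analyses descriptive and not an explicit basis for the efficacy decision. That lowers the severity. It does not remove the point, because these endpoints are meant to support that decision and the key ones are formally tested with multiplicity control.

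**Conclusion.** The contradiction stands for the key secondary binary endpoints and the additional binary efficacy endpoints. The rule chosen can change a tested result: with 4 missing, 15 successes give p = 0.154 or 0.021, and 16 give 0.076 or 0.006. A single missing subject moves 16 successes from 0.076 to 0.047.

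These figures rest on assumed missingness of 1 to 4 of 24 with no later success. The SAP gives no dropout rate, and sections 10.1 and 10.2.1 expect the endpoints to be available. With none missing the rules coincide, and whether a hypothesis is rejected also depends on the other Benjamini-Hochberg p-values. The documents therefore support saying that a result can change, not that it will.

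Severity is should-fix. A reader might infer that the trial's main conclusion is at risk, but the primary endpoint's missing-data rule in section 10.1 is clear and unaffected.

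**What to change.** - In 12.5, state that the key and additional binary efficacy endpoints follow 10.2.1 in the ITT population, with observed-data results as supportive, and that the observed-data rule applies to the remaining metabolic and QOL measures.
- State which rule applies to the Clarke change (key endpoint 8). It is continuous, so failure imputation cannot be applied to it as worded, and both sections currently cover it.
- Keep SAE- and death-related missing values in the sensitivity analysis. For the binary endpoints, count them as failures or run a tipping-point analysis.
- Correct the cross-reference to section 14, or add the missing efficacy analysis of those subjects.

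The contradiction does not require failure imputation for the MAGE, LI and HYPO cut-offs, or a return-to-baseline rule for continuous measures. The cost is a few sentences and one extra run; some secondary rates may look slightly lower.

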5.2 Study Populations

The study population consists of individuals with T1D who have had a kidney transplant and who meet the eligibility criteria for the trial described in Section 3 of the CIT-06 protocol. This section of the SAP describes three study populations. All efficacy analyses will be done on the ITT population. Parallel analyses will be done on the per-protocol population. Safety analyses will focus on the safety population.

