The insulin modified FSIGT test will be performed at 75 ± 5 days following the first and final infusion (if applicable). AIR_{glu}, SI and DI, derived from the test, provide a composite measure of β -cell function. AIR_{glu} is calculated as the incremental area-under-the-curve for insulin between 0 and 10 minutes post injection. SI, a measure of insulin-dependent glucose disposal, is derived from Bergman's minimal model using MinMod Millennium software (Pacini & Bergman, 1986) (Saad, Anderson, Laws, & al, 2004). The DI is calculated by AIR_{glu}*SI. The three variables are all continuous and will be analyzed using the method for a continuous variable.

11.11 *Glucose variability and hypoglycemia duration derived from the continuous glucose monitoring system (CGMS)*

CGMS involves the subcutaneous placement of a glucose sensor connected by tubing to a pager-sized monitoring device that stores glucose data obtained every 5 minutes over a 72-hour period (Steja, 2005). Data from a 72-hour period near the target time point will be used to derive the glucose variability and hypoglycemia duration.

The glucose variability is the standard deviation of all measured glucose values and is a continuous variable. This variable will be analyzed using the method for a continuous variable. The data from the 72-hour period are used to derive the number and duration of all hypoglycemic episodes (measured glucose < 3.0 mmol/L [54 mg/dL]). Then the total duration of hypoglycemia can be calculated. The hypoglycemia duration is a continuous variable and is analyzed using the method for a continuous variable. The distribution of the number of hypoglycemic events will be tabled.

11.12 *The percent reduction in insulin requirement*

The percent reduction from the baseline insulin requirement at each time point will be calculated. The analysis of the percent reduction adopts the method for a continuous variable.

12. Analysis of Quality of Life Measures

The analysis of QOL will be conducted for the ITT population. QOL measures are obtained every three months while the patient is on the wait list. Observed values from the last of these prior to transplant will be used as the baseline value. After transplant, QOL measures are obtained at 75 ± 5 days after each transplant (unless a subsequent transplant has occurred), and at one year, 2 years and 3 years after the first and last transplants. Separate analyses will be calculated for each measure at each time point.

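### Section 12.5 labels its missing-data sensitivity analysis missing at random but defines it as missing completely at random, names no imputation predictors, and leaves out SAE-related missing values

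*SAP*

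**What the plan says.** Section 5.2 states "All efficacy analyses will be done on the ITT population", and section 12 repeats this for quality of life: "The analysis of QOL will be conducted for the ITT population". For secondary endpoints, section 12.5 then says "we will not impute missing values in the analysis but will report results for the observed data only" and confines interpretation to subjects whose efficacy could be measured.

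The check on this is in the same section:

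- Label: "We will conduct a sensitivity analysis assuming a missing at random mechanism".
- Definition, introduced as a restatement of the label: "we assume that a subject will withdraw consent at random with probability r".
- How r is obtained: "This probability will be estimated at each time point".
- Method: "We will use the method of multiple imputation (Schafer, 1999) to develop estimates and standard errors that account for the missing data".
- What is read off: "We will compare the magnitude of the differences between multiple imputation estimates and observed data estimates".

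Section 12.5 also leaves values missing because of an SAE out of the sensitivity analysis and refers those subjects to section 14. It adds that missing at random cannot be verified and that the results call for caution. It names no predictors for the imputation and no run under a missing-not-at-random assumption.

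**The concern.** Missing at random means that missingness may depend on observed data, such as a subject's baseline or earlier post-transplant values. The definition given allows no such dependence. Everyone at a visit shares one r. That is missing completely at random, and it assumes away the problem the check is meant to examine: whether subjects who are doing badly are the ones who drop out.

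At stake is how far the observed-data summaries of the secondary outcomes can be trusted. If subjects with poor graft function leave preferentially, those summaries look too favourable. A programmer who takes the probability-r wording as the specification could fit an imputation model without predictors. The comparison would then look reassuring for reasons unrelated to the data.

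The SAE exclusion adds to this. Section 12.5 itself names SAEs as a cause of withdrawal. These missing values are plausibly the most informative, and section 14, to which they are referred, describes safety analyses only.

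**Working it through.** **No figure to reproduce.** Section 12.5 gives no value for r, so the first step is to compare definitions.

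| Mechanism | Missingness may depend on | Observed-data mean |
|---|---|---|
| Completely at random | nothing about the subject | unbiased |
| At random | observed baseline and earlier values | biased in general |
| Not at random | the unobserved value itself | biased in general |

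The wording of 12.5 fits the first row. Estimating r at each visit lets it change over time but does not tie it to subject data.

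**What the comparison would show.** Simulated trials of 24 subjects (the SAP's sample size), 6000 replicates, 10 imputations, outcome SD 1, higher values worse. Assumptions not in the SAP: about 20 to 22% missing; baseline-outcome correlation 0.6; logistic slope 1.5 on baseline (at random) or on the outcome (not at random).

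| True mechanism | Imputation model | Observed-data bias (SD) | Imputation bias (SD) | Mean difference (SD) |
|---|---|---|---|---|
| Completely at random | with or without baseline | about 0.00 | about 0.00 | 0.00 |
| At random | no predictors | -0.15 | -0.15 | 0.00 |
| At random | baseline included | -0.15 | 0.00 | +0.15 |
| Not at random | no predictors | -0.25 | -0.25 | 0.00 |
| Not at random | baseline included | -0.25 | -0.17 | +0.08 |

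With baseline included and correlation 0.3 to 0.8, the difference is 0.08 to 0.20 SD under missing at random and 0.02 to 0.15 SD under missing not at random.

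**On the HbA1c scale.** Table 4.3 gives a 12-month change of -1.5 ± 1.8 (16 subjects). Assume that 6- and 12-month changes both have this mean and SD, with correlation ρ, and that the odds of withdrawal triple per SD worse 6-month change z. Then

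observed-only mean = -1.5 + 1.8 × ρ × E[z | retained].

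Solving the logistic model for 10%, 15% and 20% withdrawal gives E[z | retained] = -0.0978, -0.1423 and -0.1855. With ρ = 0.7, 1.8 × 0.7 = 1.26:

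- 10%: -1.5 - 1.26 × 0.0978 = -1.62, overstatement 0.123/1.5 = 8%
- 15%: -1.5 - 1.26 × 0.1423 = -1.68, overstatement 0.179/1.5 = 12%
- 20%: -1.5 - 1.26 × 0.1855 = -1.73, overstatement 0.234/1.5 = 16%

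At 15% withdrawal, ρ from 0.5 to 0.8 gives 0.128/1.5 = 9% to 0.205/1.5 = 14%. Imputation conditional on the 6-month value returns about -1.50.

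**Yardstick.** Section 4.1.1 puts the 95% half-width at about 0.4 SD (1.96/√24 = 0.400). For an SD of 1.8 that is 0.72 points, against a bias of 0.12 to 0.23 points.

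**Which outcomes.** Using the cross-sectional SDs in Table 4.4, a bias of 0.15 SD would be 0.15 × 4 = 0.6 for MAGE, 0.15 × 200 = 30 for LI and 0.15 × 750 = 112.5 for HYPO score. The tabulated precisions are 1.6, 80 and 300.

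**The case against.** The strongest reply is that multiple imputation does not use r. It draws from an outcome model, and what it can reveal depends on that model's predictors. A reader might infer from the definition that the planned check is blind to bias whatever the data. The SAP does not support this: it nowhere says that baseline or earlier values are left out, and with baseline included the simulation recovers all of the missing-at-random bias and part of the rest. A reader might also take r as constant throughout, but it is estimated at each visit. What stands is that the only mechanism written down has no covariates and the model is left open.

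The SAP also has other analyses. The mixed models in 12.3.1 (extended to the other quality-of-life scales) and in 13.1 (HbA1c, insulin requirement, Clarke score, glucose, C-peptide and others) use earlier visits and are valid under missing at random, and 13.1 mentions multiple imputation again. This covers much of the ground, including HbA1c. However, MAGE, LI and HYPO score are absent from the 13.1 list. They appear in 13.2 and 13.3, but for comparisons with waitlisted subjects or with pre-transplant profiles.

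The consequence is limited too. Section 10.2 calls the secondary analyses descriptive and not the basis for the efficacy decision. Missing primary and key secondary results have their own rules in 10.1 and 10.2.1, broadly failure unless later data show otherwise. The caveat in 12.5 is proper, but it is not a test of departures from the assumption.

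**Conclusion.** The label and the definition conflict. Under the definition as written, observed-data analysis is already unbiased, so that assumption does not challenge the analysis it should test. Whether the check works depends on a choice the SAP leaves open. No missing-not-at-random run is planned for these outcomes, and SAE-related missing values are excluded from the check.

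The scope is the secondary outcomes governed by 12.5, mainly the continuous ones. Key binary endpoints are imputed as failures under 10.2.1, and 10.2.2 carries the same analysis to the additional efficacy endpoints. The change in Clarke score is unclear between 10.2.1 and 12.5. The gap matters most for MAGE, LI and HYPO score.

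The definitional conclusion needs no assumption. The sizes do: 8 to 16% of the HbA1c change rests on an assumed withdrawal rate, odds ratio and correlation, and the bias is well inside the SAP's own precision. This should be corrected, but it does not threaten the trial's primary conclusion.

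**What to change.** In section 12.5:

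1. Replace the two probability-r sentences with a statement that missingness at a visit may depend on baseline and earlier observed values.
2. Name a small imputation model for each continuous outcome: its baseline value plus the most recent one or two earlier values of the same outcome. About 24 subjects will not support more. For MAGE, LI and HYPO score, Appendix 8 already provides for Day 75 values.
3. Include SAE-related missing values in the sensitivity analysis.
4. Add one delta-adjusted run in which imputed changes worsen progressively to no change from baseline, and report where the reading of the result would alter.
5. State whether 10.2.1 or 12.5 governs a missing Clarke score change.

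The cost is SAP wording, a few extra runs on data already collected, and slightly wider intervals.
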